5 STUDY DRUGS

All study drug supplied by the Sponsor must be stored in a secure location accessible only to designated study personnel.

5.1 Description of Study Drugs

In Part A (and previously in Part B of the study which was discontinued), TD-9855 will be provided by the Sponsor as a bulk active pharmaceutical ingredient (API), appearing as a white powder. Doses for individual subject administration will be prepared as a solution in filtered apple juice by the designated unblinded pharmacist at the CRC. In Part C, TD-9855 will be provided as a [REDACTED] packaged in open-labeled 40-count high density polyethylene bottles. Detailed storage and preparation instructions will be provided in a separate pharmacy manual.

5.2 Dosage and Administration

Part A Dose Escalation

On Day -2 of Part A, eligible subjects will be admitted to the CRC, where they will remain during the entire dose escalation period. On Day 1, subjects will receive a single dose of placebo in a single-blind manner (ie, subject remains blinded). This will be followed by daily dose escalations, beginning with [REDACTED] TD-9855 on Day 2. On each subsequent day, subjects will receive a single escalating dose of TD-9855 [REDACTED] [Day 3], [REDACTED] [Day 4], and [REDACTED] [Day 5]) until Day 5 or until reaching the preset stopping criteria described below, whichever occurs first.

The stopping criteria are:

- A determination from the Investigator (in collaboration with the Sponsor) that administration of the subsequent dose may pose a safety concern
- SBP \geq 180 mm or DBP \geq 110 mm in the sitting position replicated 2 more times over an hour
- Intolerable side effects as determined by the Investigator

- Received maximum dose of study medication specified by the protocol

Once the subject meets any of the above criteria, no further dose escalation will be performed. However, based on the daily evaluation of tolerability, the Investigator (in collaboration with the Sponsor), may decide to not escalate the dose, but rather re-administer the previous dose from the prior day. Once the decision has been made to not escalate the dose, the subject should remain at the current dose through Day 5 of dosing. Following a post dosing observation day in the clinic, the subject will have discharge procedures completed and will be released from the CRC.

Subjects who do not demonstrate a clinically meaningful pressor effect based on Investigator determination (in collaboration with the Sponsor), or who discontinue study drug prior to reaching the stopping criteria, should have discharge procedures completed, but will not continue to Part C of the study.

Washout Period

Following the completion of Part A, subjects will be discharged from the CRC and undergo a washout period (minimum 8 days). On a daily basis following the first 72 hours from discharge, and then at least weekly during the first 4 weeks after discharge, the Investigator or designee will contact the subject by telephone to review the subject's health status. Any adverse events reported by phone will be recorded and followed as medically appropriate determined by the Investigator. Under the direction of the Investigator, subjects will manage their nOH symptoms using fludrocortisone as prescribed.

Part B – Randomized Parallel Design

In Part B, refer to prior versions of this Protocol for specific information related to Part B which was discontinued in Amendment 2.

Part C – Outpatient Extension

The dose level administered on Day 1 in Part C will be equal to 50% of the highest tolerated dose level (rounded-up to the nearest 1 mg) administered during Part A for that subject (or a lower dose at the discretion of the principal investigator to manage individual subject safety). Subjects will be discharged from the research clinic on Day 2, and continue at the same dose level as Day 1 of Part-C. At the subsequent scheduled visits until Day 29, the Investigator has the option to double the subject's dose level at their discretion, if in their opinion the subject will benefit from, and can tolerate, a higher dose level. After Day 29,

dose increases will need to be discussed with the Sponsor. It is recommended that the subject receives at least 7 daily doses of TD-9855 at any single dose level before escalation to a higher dose to allow TD-9855 exposure to reach steady state at the lower dose. [REDACTED]

[REDACTED] The maximum dose administered to any subject is [REDACTED]. The schedule for potential dose increases is shown below in Table 3.

Table 3: Weekly Dose Escalation Plan for Subject in Part C

Part A Maximum Dose	Part C Day 1 dose	Part C Day 8 dose	Part C Day 15 dose	Part C Day 22 dose	Part C Day 29 dose
[REDACTED]	[REDACTED]	[REDACTED]	[REDACTED]	[REDACTED]	[REDACTED]
[REDACTED]	[REDACTED]	[REDACTED]	[REDACTED]	[REDACTED]	[REDACTED]
[REDACTED]	[REDACTED]	[REDACTED]	[REDACTED]	[REDACTED]	[REDACTED]

In the case where a subject develops the presence or worsening of supine hypertension (as determined by the Investigator with agreement from the Sponsor) or other adverse events suggesting intolerance, the dose can be withheld for 3 days and resumed at a dose level 50% (rounded up to the nearest 1 mg) of the prior dose level. If supine hypertension or other adverse events persist after the dose has been reduced, dosing in that subject should be discontinued and appropriate alternative therapy and care provided to the subject as determined by the principal investigator.

In Part A, subjects will be administered study drug by qualified study personnel under the supervision of the Investigator. Study personnel will observe and record date and time of dosing and in the event any deviations or incomplete administrations will be noted in the source records.

In Part C, subjects will be administered study drug by qualified study personnel under the supervision of the Investigator on Day 1 and Day 2. On all other dosing days, subjects will record the date and time of their daily dose in a dosing diary. Any dose increases, missed doses, or issues with dosing should be noted in the dosing diary. Site staff will also record any dose increase in the subject's source documents. Subjects are expected to bring the

dosing diary and any empty and/or partially used bottles of study drug to the clinic on their return visits.

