This is a multicenter, randomized, 3 part, single-blind (Part A), double-blind (Part B), and open-label multiple dose extension (Part C) study of TD-9855 versus placebo in subjects with nOH. However, beginning with Amendment 2 of this protocol, Part B of the study has been discontinued. Therefore, any new subjects enrolled after Amendment 2 will not be enrolled in Part B. Details regarding Part B are still included in this document but where appropriate the reader is referred to prior version of this protocol for more specific information related to Part B.

This study now consists of 2 Parts, A and C. Part A follows a daily, single, escalating dose design starting with placebo on Day 1, followed by a dose of [REDACTED] TD-9855 on Day 2, and proceeding to escalating higher doses of TD-9855 on a daily basis up to a maximum dose of [REDACTED] based on safety, tolerability, and determination of a pressor effect. In Part C, subjects who demonstrate a pressor effect in Part A, who complete Part A, and remain otherwise eligible will have the option to receive open-label TD-9855 by tablet daily for up to [REDACTED]

Study Procedures:

Part A – Dose Escalation

On Day -2 of Part A, eligible subjects will be admitted to the clinical research center (CRC), where they will remain during the entire dose escalation period. On Day 1, subjects will receive a single dose of placebo in a single-blind manner (ie, subject remains blinded). This will be followed by daily single-blind dose escalations, beginning with [REDACTED] of TD-9855 on Day 2. On each subsequent day, subjects will receive a single escalating dose of TD-9855

PROTOCOL SYNOPSIS (CONTINUED)

[REDACTED] [Day 3], [REDACTED] [Day 4], [REDACTED] [Day 5]) until Day 5 or until reaching the preset stopping criteria described below, whichever occurs first. The stopping criteria are:

- A determination from the Investigator (in collaboration with the Sponsor) that administration of the subsequent dose may pose a safety concern
- SBP \geq 180 mm or DBP \geq 110 mm in the sitting position replicated 2 more times over an hour
- Intolerable side effects as determined by the Investigator
- Received maximum dose of study medication specified by the protocol

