Once the subject meets any of the above criteria, no further dose escalation will be performed. However, based on the daily evaluation of tolerability, the Investigator (in collaboration with the Sponsor), may decide to not escalate the dose, but rather re-administer the previous dose from the prior day. Once the decision has been made to not escalate the dose, the subject may remain at the current dose through Day 5 of dosing. Following a post dosing observation day in the clinic, the subject will have discharge procedures completed and will be released from the CRC.

Subjects who do not demonstrate a clinically meaningful pressor effect based on Investigator determination (in collaboration with the Sponsor), or who discontinue study drug prior to reaching the stopping criteria, should have discharge procedures completed, but will not continue to study Part C.

Washout Period

Following the completion of Part A, eligible subjects will be discharged from the CRC and undergo a washout period [REDACTED]. On a daily basis during the first 72 hours from discharge, and then weekly for the first 4 weeks after discharge from Part A during the washout period, the Investigator or designee will contact the subject by telephone to review the subject's health status. Any adverse events reported by phone will be recorded and followed as medically appropriate determined by the Investigator. Under the direction of the Investigator, subjects will manage their nOH symptoms using fludrocortisone as prescribed.

Part B – Randomized, Double-blind, Parallel Design

Beginning with Amendment 2 of this protocol, Part B of the study has been discontinued. Refer to prior versions of this protocol for specific details regarding Part B.

Part C – Open Label Extension

In Part C, subjects who demonstrate a pressor effect in Part A, who complete Part A and remain otherwise eligible will have the option to participate in Part C and receive open-label TD-9855 by tablet once daily for up to [REDACTED].

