- Duration of standing during the orthostatic standing test

The secondary endpoints for Part C include:

- The composite OHSA and OHDAS score.
- Change from time-matched placebo in standing SBP
- Change from time-matched placebo in seated SBP (area under the curve for 0-12 hours following drug administration).
- Duration of standing during the orthostatic standing test

PROTOCOL SYNOPSIS (CONTINUED)

For all Parts of the study, safety and tolerability assessments will include adverse events, laboratory abnormalities, ECGs, and vital sign measurements including supine blood pressure. Exploratory PK and PD analysis will also be performed for all parts of the study.

Analysis:

All analyses will be presented separately by part.

SCHEDULE OF STUDY ASSESSMENTS

Table 1: Schedule of Study Procedures/Assessments – Part A

Procedure	Screening (Day -30 to -1)	Admission (Day -2)	Admission (Day -1)	(Day 1 ^a)	Dose Escalation (Day 2 - 5)	Discharge (Day 3, 4, 5, or 6) ^b	Washout Min (8 days)
Overnight residency and Standardized Meal		X	X	X	X		
Informed Consent (may be signed up to 30 days prior to screening)	X						
Review Inclusion/Exclusion Criteria	X		X				
Medication and Medical History	X	X ^c	X ^c				
Height/Weight/BMI ^d	X		X ^d	X ^d	X ^d	X ^d	
Temperature and respiratory rate	X ^q		X ^q	X ^q	X ^q	X ^q	
Autonomic Function Testing ^e	X ^e						
Orthostatic Standing Test ^f	X ^f		X ^f	X ^f	X ^f	X ^f	
Supine Blood Pressure (after supine for 10 mins) ^g				X ^g	X ^g		
ECG (12-lead) ^h	X ^h		X ^h	X ^h	X ^h	X ^h	
Physical Examination ⁱ	X ^g		X ⁱ	X ⁱ	X ⁱ	X ⁱ	
Pregnancy Test (females only) ^j	X ^j						
Hematology, Serum Chemistry, and Urinalysis	X		X			X	
Urine Drug Screen	X						
Urine Collection and Volume Measurement			X ^k	X ^k	X ^k	X ^k	
PK Sampling ^l					X ^l	X ^l	
PD Sampling: NE and DHPG ^m				X ^m	X ^m	X ^m	
OH Questionnaire (OHSA) ⁿ	X ⁿ		X ⁿ	X ⁿ	X ⁿ	X ⁿ	
Clinician's/Subject's Global Impression ^p			X ^p	X ^p	X ^p	X ^p	
Concomitant Medications	X	X	X	X	X	X	
Adverse Events ^o	X	X	X	X	X	X	X ^o
Study Drug Administration (placebo/TD-9855)				X	X		

a. Study Day 1 is defined as the day of first study dosing (placebo). The preceding day is Study Day -1. Note that there is no Study Day 0.

b. Actual day of discharge will be on day following preset stopping criteria.

c. History update, if any changes since the Screening Visit, will be obtained.

SCHEDULE OF STUDY ASSESSMENTS (CONTINUED)

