3.1 Overview

This is a multicenter, randomized, 3 part, single-blind (Part A), double-blind (Part B), and open-label multiple dose extension (Part C) study of TD 9855 versus placebo in subjects with nOH. However, beginning with Amendment 2 of this protocol, Part B of the study has been discontinued. Therefore, any new subjects enrolled after Amendment 2 will not be enrolled in Part B. Details regarding Part B are still included in this document but where appropriate the reader is referred to the prior version of this protocol for more specific information related to Part B.

This study now consists of 2 Parts, A and C. Part A follows a daily, single, escalating dose design starting with placebo on Day 1, followed by a dose of [REDACTED] TD-9855 on Day 2, and proceeding to escalating higher doses of TD-9855 on a daily basis up to a maximum dose of [REDACTED] based on safety, tolerability, and determination of a pressor effect. In Part C, subjects who demonstrate a pressor effect in Part A, who complete Part A, and remain otherwise eligible will have the option to receive open-label TD-9855 by tablet daily for up to [REDACTED]

Study Schematics

[figure not shown]
Part A – Single Blind, Dose-Escalation

Part B

Beginning with Amendment 2, Part B has been discontinued. Refer to prior versions of this protocol regarding more specific information pertaining to Part B.

Part C

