6.3.2 Overnight Residency, Standardized Meals, and Restrictions

Subjects will be admitted and remain resident in the clinical research center (CRC) beginning Day -2 through the morning of Day 6 in Part A, and Day -2 through the morning of Day 2 for Part C.

[REDACTED]

[REDACTED]

[REDACTED]

[REDACTED]

[REDACTED]

Should there be a clinically significant change between Screening and Day 1 of either Part A or Part C such that subjects no longer meet the eligibility criteria, they will no longer be eligible for the study and should be listed as a screen failure.

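### The Part A text does not consistently say whether meeting a stopping criterion ends dosing or only ends escalation

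*Protocol*

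**What the plan says.** Five places in the protocol bear on this.

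- **Synopsis (Part A) and section 5.2, schedule.** Placebo is given on Day 1 and active drug from Day 2. Single escalating doses follow daily "until Day 5 or until reaching the preset stopping criteria described below, whichever occurs first". Section 3.5.2 has a shorter form of the same rule.
- **Section 5.2 and the synopsis, effect of a criterion.** Four criteria are listed: an Investigator-with-Sponsor judgement that the next dose may be unsafe; replicated seated SBP of at least 180 or DBP of at least 110; intolerable side effects; and reaching the protocol maximum dose. Then: "Once the subject meets any of the above criteria, no further dose escalation will be performed".
- **Section 5.2, the option that follows.** A sentence opening with *However* says that the Investigator, with the Sponsor, "may decide to not escalate the dose, but rather re-administer the previous dose from the prior day". Next comes: "Once the decision has been made to not escalate the dose, the subject should remain at the current dose through Day 5 of dosing". Section 3.5.2 also uses *should*. The synopsis says "the subject may remain at the current dose through Day 5 of dosing".
- **Table 1.** The discharge column is headed Day 3, 4, 5 or 6, and footnote b reads: "Actual day of discharge will be on day following preset stopping criteria". The study drug row has no mark in the discharge column.
- **Section 6.3.2.** Subjects are resident "beginning Day -2 through the morning of Day 6 in Part A".

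**The concern.** A site whose subject has a replicated seated SBP of 180 on Day 3 can find two answers. Table 1 sends the subject home on Day 4 with no further dose. Section 5.2, read straight through, stops only the increase, offers a repeat of the Day 3 dose, and then says the subject should stay on it through Day 5.

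The criteria are safety events. Section 1.4 lists an increase in BP as an important potential risk, and section 8.5 says there is no data monitoring committee. Exclusion criterion 4 still provides for new Part A subjects under Amendment 3, so the wording governs subjects yet to be dosed. What is at stake is exposure after a safety signal, and whether similar subjects are handled alike.

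**Working it through.** **Inputs.** First active dose on Day 2 and last scheduled dose on Day 5 (synopsis, 5.2). Discharge days 3 to 6 and footnote b (Table 1). Hold through Day 5 (synopsis, 3.5.2, 5.2). No redacted figure is needed for steps 1 to 3.

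**Step 1: reproduce the plan's discharge days.** Let d be the day a criterion is met. Under footnote b, discharge day = d + 1. For d = 2, 3, 4, 5 this gives Day 3, 4, 5, 6, exactly the Table 1 column heading. Since Table 1 schedules no drug on the discharge day, further doses = 0 for every d.

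**Step 2: apply the hold sentence instead.** If the subject stays on the same dose through Day 5, further doses = 5 − d, and discharge is always Day 6.

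| Criterion met on | Table 1 footnote b: further doses / discharge | Hold through Day 5: further doses / discharge |
|---|---|---|
| Day 2 | 0 / Day 3 | 3 / Day 6 |
| Day 3 | 0 / Day 4 | 2 / Day 6 |
| Day 4 | 0 / Day 5 | 1 / Day 6 |
| Day 5 | 0 / Day 6 | 0 / Day 6 |

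The two agree only for Day 5.

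**Step 3: does the text keep the two paths apart?** Set the first stopping criterion beside the elective hold. Both are made by the Investigator together with the Sponsor. Both look ahead to the next dose. One rests on a possible safety concern, the other on the daily tolerability evaluation. The same decision can be recorded as criterion 1, with discharge next day under Table 1, or as an elective hold, with dosing through Day 5. No sentence says that the hold is closed to a subject who has met a criterion, and in both 5.2 and 3.5.2 it follows the stopping-criteria text directly.

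**Step 4: illustrate the exposure (assumed half-life).** Section 3.5.2 recommends at least 7 daily doses at a level so that steady state is reached, and warns that several increases within 7 days could more than double exposure. No half-life is given. Assume linear kinetics and that 7 daily doses reach a fraction f of steady state, with f between 0.90 and 0.97.

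- Daily retention r = (1 − f)^(1/7): 0.10^(1/7) = 0.72 and 0.03^(1/7) = 0.61, which are half-lives of about 2.1 and 1.4 days.
- Criterion on Day 2 with three repeats, so four equal doses: (1 − r⁴)/(1 − r) = 2.61 at r = 0.72 and 2.20 at r = 0.61, relative to the first dose.

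A criterion met on Day 3 or 4 would also need the redacted earlier doses.

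**The case against.** The strongest reply is that 5.2 describes two branches. Meeting a criterion is one. The elective hold is the other, with its own trigger (the daily tolerability evaluation), and the hold sentence attaches to the decision not to escalate, not to a criterion. Other text fits this. Subjects who come off drug before reaching the criteria are barred from Part C, which treats the criteria as a normal end of dosing. Table 1 footnotes l and m tie the last PK and PD samples to the final dose after the criteria are reached or at the end of the sequence. On that reading 5.2 and Table 1 agree. It is plausible, but the reader has to supply it, and the overlap with criterion 1 remains.

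Several stronger inferences are tempting and should not be drawn.

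- *The protocol requires redosing after a hypertensive reading.* It does not. Repeat dosing is a discretionary choice made with the Sponsor, and section 6.4.1 lets the Investigator discontinue a subject at any time.
- *Repeat dosing alters the Part C starting dose.* That dose is half of the highest tolerated Part A level. Repeating a level does not by itself raise it, and escalation stops at the same level on either reading.
- *Section 6.3.2 flatly contradicts Table 1.* It may describe only the full-course stay, and lines in that section are redacted.
- *The overview adds a fifth stopping rule.* Section 3.1 says escalation is "based on safety, tolerability, and determination of a pressor effect", and no listed criterion is a pressor effect. This is a loose summary line, worth aligning but minor.
- *A Part A analysis is damaged.* The SAP covers Part C only and the protocol's efficacy analysis is redacted, so no such effect can be shown.

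**Conclusion.** The point stands as an internal wording conflict on a safety-relevant rule. After a criterion on Day 2, 3 or 4, the documents allow a reading with no further active dose and a reading with up to 3, 2 or 1. The maximum of three needs a criterion to be met on the first active dose. These counts come from the stated schedule alone. The *may*/*should* difference stands even on the two-branch reading.

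The roughly 2.2- to 2.6-fold figure is illustrative only. It rests on an assumed half-life and linear kinetics, and the conflict does not depend on it. The redacted text and missing schematics could contain a clarifying line, but the operative sentences in the synopsis, 3.5.2, 5.2 and Table 1 are legible and do not settle the matter. Nothing here says which rule is clinically right.

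**What to change.** Reconcile the synopsis, Table 1 with footnote b, and sections 3.5.2, 5.2 and 6.3.2 so that one rule applies:

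- for each of the four stopping criteria, state whether it ends dosing or ends escalation only;
- set the elective repeat-dose option apart from the criteria, and say whether it is open to a subject who has met one;
- distinguish criterion 1 from the elective hold, or merge them;
- use one verb (*may* or *should*) throughout;
- align the discharge days and the residency period with the chosen rule;
- at the same time, make the pressor-effect phrase in the synopsis and 3.1 agree with the criteria list.

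The sponsor decides which rule applies. The cost is wording in an amendment or clarification letter, with no new procedure or data collection.

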5.3 Drug Accountability and Reconciliation

The unblinded pharmacist or designee is responsible for maintaining accountability records for all study drug(s) received from the Sponsor, in accordance with applicable government regulations and study procedures. The accountability records for study medication (TD-9855) will be maintained in a secure location, accessible only to authorized staff members. The accountability record will include entries for receipt, distribution or dispensing, and destruction of the material(s).

The pharmacist must retain all unused, and expired product until the site monitor has confirmed accountability data. No study drug (used, partially used, and unused bottles) may be destroyed without prior approval from the Sponsor. Compliance with the dosing regimen will also be assessed by reconciliation of used and unused study drug.

Unused and expired study drugs will be disposed of in accordance with written instructions from the Sponsor. Copies of the study medication accountability records will be provided to the Sponsor at completion of the study and will be made available for review by the site monitor during the course of the study.

